6.4 Halting Rules

Further enrollment and study vaccinations will be halted (paused) for SMC review/recommendation if any of the following are reported:

- Any subject experiences ulceration, abscess, or necrosis in the nose that is considered to be related to study product administration, through 28 days following the boosting vaccination.
- Any subject experiences laryngospasm, bronchospasm, or anaphylaxis within 1 day after administration of study vaccination that is considered to be related to study vaccination.
- Three or more subjects experience generalized urticaria grade 3 or higher within 3 days after administration of study vaccination that is considered to be related to study vaccination.
- Any subject experiences a study product-related SAE from the time of the primary vaccination through the subject's last study visit on Day 254.
- Any subject experiences acute weakness of limbs and/or cranial nerve innervated muscles (description of potential signal of Guillain-Barré syndrome) after administration of study vaccination, through 28 days following the boosting vaccination.

This study will also be halted for SMC review/recommendation if, within 8 days after administration of each study vaccination, the following occurs:

- 5% of subjects experience the same severe study product-related subjective systemic, local, or mucosal reaction, for which the severity (grade) is corroborated by study personnel.

Grading scales for solicited reactions are included in [Section 6.3.5.3](#).

If any of the halting rules are met following any subject receipt of study vaccination, then this study will not continue with the remaining enrollments or future vaccination without a review by and recommendation from the SMC to proceed. Vaccination windows will be adjusted for any such pause to allow subjects to remain within the expected schedule of events. All events that classify for halting rules will be entered as adverse events.

ILiAD retains the authority to suspend additional enrollment and study interventions or administration of study product during the entire study, as applicable.

6.5 Pregnancy

Pregnancy is not regarded as an AE unless there is a suspicion that an investigational vaccine may have interfered with the effectiveness of a contraceptive medication. Any pregnancy that occurs during study participation must be reported using a clinical study pregnancy form. To ensure subject safety, each pregnancy must be reported to the sponsor, ILiAD Biotechnologies, within 2 weeks of learning of its occurrence. If pregnancy occurs further vaccination will be discontinued. The pregnancy must be followed-up to determine outcome (including spontaneous miscarriage, elective termination, normal birth, or congenital abnormality) and status of mother and child, even if the subject was discontinued from the study. Pregnancy complications and elective terminations for medical reasons must be reported as an AE or SAE. Spontaneous miscarriages must be reported as an SAE.

Any pregnancy, brought to the investigator's attention after the subject has completed the study, but occurring while the subject was in the study, must be promptly reported to ILiAD Biotechnologies.

6.6 Laboratory Analyses

Any abnormal laboratory test results (hematology, chemistry, or coagulation) resulting in a grade 3 or greater toxicity score which is associated with the scheduled safety cohort follow up testing must be entered as an adverse event and followed with retesting and observing for resolution. If an underlying disease or new condition is identified that accounts for the elevation than this should be documented as the adverse event.

Any clinically significant safety assessments that are associated with the underlying or new onset condition for which laboratory testing occurs during the course of the study will not be

entered as adverse events per se, rather the new onset or worsening condition should be entered as judged by the investigator.

6.7 Sample Collections

Procedures for the handling and processing of biological samples are provided in the Laboratory Manual or the Site Manual.

The hematology, coagulation, and chemistry laboratory analyses will be performed at a central laboratory. Laboratory data will be graded according to the FDA Toxicity Grading Scale (Table 13-2) and will be adjusted according to local laboratory reference ranges.

The samples collected for immunogenicity (B and T cell) testing and pertussis culture will be stored in appropriate conditions as specified in the Laboratory Manual until shipped for testing at a facility designated by the sponsor.

Subjects will be asked to provide a signed informed consent for the use of samples for further pertussis-specific testing or assay development. Aliquots of collected samples from this study may be retained for additional testing of antigens specific to *B. pertussis* for a maximum of 10 years (starting from the date at which the last subject had the last study visit), unless local rules, regulations, or guidelines require different timeframes or different procedures, in accord with subject consent. Testing for colonization using *B. pertussis* culture following the primary vaccination and post-boosting vaccination will also occur.

7 Statistical and Analytical Plan

The primary objectives of this study are to assess nasal mucosal immune response S-IgA following intranasal vaccination with BPZE1 (10^9 CFU) when used as a single (eg, prime) or 2-dose (eg, prime + boost) series and reactogenicity (all) and specific safety laboratory parameters (safety lead-in cohort only) following intranasal vaccination with BPZE1 (10^9 CFU), in healthy volunteers 18 to 50 years of age. This study is designed as a randomized, placebo-controlled, observer-blinded clinical trial evaluating the safety and immunogenicity of 1 or 2 doses of 10^9 CFU of BPZE1 delivered by intranasal VaxINator device or Boostrix delivered by IM injection. To maintain the blind, placebo vaccination via IM and intranasal routes will be included.

The primary database lock will occur on Day 113 and all data collected through Day 113 will be included in the CSR and submitted to regulatory authorities. A subsequent longer-term safety follow-up, including longer-term persistence of immune responses, will occur through Day 254. These data will be provided in an addendum to the CSR. The clinical site study team directly participating in subject contact/care will remain blinded to the treatment assignment during this extended safety follow up period. All unblinded data analyses prior to primary database lock at Day 113 will be handled by the unblinded team of statisticians and programmers. A strict firewall between the blinded and unblinded teams will be maintained during study conduct.

This Phase 2b study is not designed to test a formal null hypothesis. Rather, it is intended to obtain preliminary assessment of the safety and immunogenicity induced by the BPZE1 lyophilized vaccine in healthy adults.

7.1 Primary Immunogenicity and Safety Endpoints

Immunogenicity:

- **Mucosal seroconversion (nasal mucosal secretion sampling):** Proportion of subjects who achieve seroconversion against at least 1 pertussis antigen (PT, FHA, PRN, FIM 2/3, or BPZE1 whole cell extract) in nasal secretions on Day 29 or 113 (prime or prime + boost).

Mucosal seroconversion is defined as a 2-fold increase over the baseline value (collected during screening) or a 4-fold increase over the minimal limit of assay detection

(whenever the baseline value falls below the limits of assay detection) for any of the pertussis-specific antibodies (S-IgA ELISA): PT, FHA, PRN, FIM 2/3, or BPZE1 whole cell extract). Seroconversion will be calculated based on absolute titer response over baseline **and** by standardizing pertussis-specific ELISA responses relative to non-pertussis-specific total nasal mucosal secretion (eg, IgA). To be further defined during assay development and within the statistical analysis plan.

Mucosal baseline samples will be taken at the screening visit.

Safety:

- Solicited AEs (local, nasal/respiratory, and systemic reactogenicity events) for 7 days following each vaccination by severity score, duration, and peak intensity. Local reactogenicity will only be monitored following the IM vaccination.
- Safety laboratory results (serum chemistry, hematology, coagulation) by FDA toxicity score (change from baseline or absolute toxicity score as defined in Table 13-2) in the safety lead-in cohort at Day 8 following each vaccination. In the case of no toxicity classification the score of 0 will be assigned.

7.2 Secondary Immunogenicity and Safety Endpoints

Systemic Immunogenicity (serum sampling [expressed separately for IgG, IgA, and IgG or IgA ELISA when possible]):

- Proportion of subjects who achieve seroconversion against pertussis antigen (PT, FHA, PRN, FIM 2/3, or BPZE1 whole cell extract) over baseline for:
 - At least 1 antigen **on each** of the Days 29, 85, 113, 169, or 254
 - At least 1 antigen **on any** of the Days 29, 85, 113, 169, or 254
 - At least **any 1** antigen **on all** Days 29, 85, 113, 169, or 254

Systemic seroconversion is defined as a 2-fold increase over the baseline value or a 4-fold increase over the minimal limit of assay detection (whenever the baseline value falls below the limits of assay detection). Both IgG and IgA ELISA will measure antibodies against the following pertussis-specific antigens of PT, FHA, PRN, and FIM 2/3, and IgG ELISA will measure antibodies against broader pertussis-specific antigens in BPZE1 whole cell extract.

Serum baseline samples will be taken at Day 1 prior to vaccination.

- Proportion of subjects who achieve seroconversion (IgG ELISA only) against BPZE1 whole cell extract over baseline:
 - On **either** Day 29 (prime) or 113 (boost)
 - On **both** Days 29 (prime) and 113 (boost).
- Proportion of subjects who achieve seroconversion against the aP antigens PT, FHA, and PRN over baseline:
 - On **either** Day 29 (prime) or 113 (boost)
 - On **both** Days 29 (prime) or 113 (boost).
- Proportion of subjects who achieve seroconversion against 2 or more pertussis antigens (PT, FHA, PRN, FIM 2/3, and BPZE1 whole cell extract) over baseline:
 - On **each** of the Days 29, 85, 113, 169, or 254
 - On **any** of the Days 29, 85, 113, 169, or 254
 - At least **the same 2 antigens** on **all** Days 29, 85, 113, 169, and 254.
- Proportion of subjects who demonstrate boosting for each pertussis antigen (PT, FHA, PRN, FIM 2/3, and BPZE1 whole cell extract) on Day 113. Boost is defined as at least a 2-fold increase from the pre-boost sample taken on Day 85.
- The GMFR against each pertussis antigen (PT, FHA, PRN, FIM 2/3, and BPZE1 whole cell extract):
 - On Days 29, 85, 113, 169, and 254 **over baseline** (Day 1)
 - On Days 113, 169, and 254 **over pre-boost** (Day 85)
 - The maximum **over baseline** on either Day 29 or 85 (post-priming response)
 - The maximum **over pre-boost** (Day 85) on any of the Days 113, 169, or 254 (post-boost response)
 - The maximum **during** the study.

- The GMT against each pertussis antigen (PT, FHA, PRN, FIM 2/3, and BPZE1 whole cell extract):
 - On Days 29, 85, 113, 169, and 254
 - The maximum on Day 29 or 85 (**after priming** dose)
 - The maximum after Days 113, 169, or 254 (**after boosting** dose)
 - The maximum **during** the study.

Mucosal Immunogenicity S-IgA ELISA (nasal mucosal secretion sampling):

- Proportion of subjects who achieve seroconversion against any pertussis-specific antigen (PT, PRN, FHA, FIM 2/3, or BPZE1 whole cell extract) over baseline:
 - At least 1 antigen **on each** of the Days 29, 78, 113, 169, or 254
 - At least 1 antigen **on any** of the Days 29, 78, 113, 169, or 254
 - At least **any** 1 antigen **on all** Days 29, 78, 113, 169, and 254.
- Proportion of subjects who achieve seroconversion against BPZE1 whole cell extract over baseline:
 - On **either** Day 29 (prime) or 113 (boost)
 - On **both** Days 29 (prime) and 113 (boost).
- Proportion of subjects who achieve seroconversion against aP antigens PT, FHA, and PRN over baseline:
 - On **either** Days 29 (prime) or 113 (boost)
 - On **both** Days 29 (prime) and 113 (boost).
- Proportion of subjects who achieve seroconversion for any 2 or more pertussis antigens (PT, PRN, FHA, or BPZE1 whole cell extract) over baseline:
 - On **each** of Days 29, 78, 113, 169, or 254
 - On **any** of Days 29, 78, 113, 169 or 254
 - At least the **same 2 antigens** on **all** Days 29, 78, 113, 169, and 254.

- Proportion of subjects who demonstrate boosting against each pertussis antigen (PT, FHA, PRN, FIM 2/3, and BPZE1 whole cell extract) on Day 113. Boost is defined as at least a 2-fold increase from pre-boost sample taken at Day 78.
- The GMFR against each pertussis antigen (PT, FHA, PRN, FIM 2/3, and BPZE1 whole cell extract):
 - On Days 29, 78, 113, 169, and 254 **over baseline** (Day 1)
 - On Days 113, 169, and 254 **over pre-boost** (Day 78)
 - The maximum **over baseline** on either Day 29 or 78 (post-priming response)
 - The maximum **over pre-boost** (Day 78) on any of the Days 113, 169, or 254 (post-boost response)
 - The maximum **during** the study.
- The GMT against each pertussis antigen (PT, FHA, PRN, FIM 2/3, and BPZE1 whole cell extract):
 - On Days 29, 78, 113, 169, and 254
 - The maximum on Days 29 or 78 (**after priming** dose)
 - The maximum after Days 113, 169, or 254 (**after boosting** dose)
 - The maximum **during** the study.

Colonization:

- Proportion of subjects with positive *B. pertussis* by bacterial culture of nasal sample collected on each day and on any day (Days 92, 96, and 113).
- *B. pertussis* colony counts on each day (Days 92, 96, and 113).
- Number of subjects who remain culture positive for *B. pertussis* at Days 78 (following priming) and 254 (following boost).

Safety:

- Unsolicited AEs (eg, treatment-emergent AEs, SAEs, and SUSARs) collected for 28 days following each vaccination by MedDRA classification and severity score.

- Unsolicited AEs related to vaccination through Day 113 by MedDRA classification and severity score.
- Serious AEs, through 6 months following the last vaccination (or until resolved or stable) by MedDRA classification, relatedness, and severity score.
- Vital sign measurements with severity scoring immediately following vaccination.

7.3 Exploratory Endpoints

- Cell-mediated (eg, B cell, CD4 T lymphocytes + T cell, CD8 T lymphocytes + T cell) responses (eg, cell staining, cytokine production) following stimulation of PBMCs collected at baseline, and 8 days post-vaccination (prime and boost) to pertussis-specific antigens. Results expressed both as absolute values and fold over baseline (per specific assay characteristics).
- Following the outcomes of the primary and secondary analyses, additional exploratory endpoints may be tested for systemic or nasal mucosal immunogenicity (IgG or IgA) responses at any time point collected and not already performed in the primary or secondary analysis sets.
- The GMT, expressed for serum IgG ELISA against tetanus and diphtheria on Days 29 and 113.

7.4 Sample Size Calculations

A total of 300 subjects will be globally assigned at 2:2:1:1 allocation ratio and receive BPZE1 intranasal administration with placebo IM or Boostrix IM with placebo intranasal administration on Day 1 and BPZE1 or placebo intranasal administration on Day 85 (See [Section 5.2](#)). This sample size is based on clinical considerations but not a statistical power analysis as the study does not test any formal null hypothesis. Table 7-1 presents the width of 95% CI for selected certain sample sizes under response rate assumptions (defined based on nasal mucosal immunogenicity) between 50% and 90%. Calculations were performed using PASS v12.

Table 7-1 95% Confidence Interval and Width for Selected Response Rate Assumptions for Relevant Treatment Arm Sample Sizes

Response Rate (%)	N = 50		N = 100		N = 200		N = 250	
	CI (%)	Width (%)						
50	35.5, 64.5	28.9	39.8, 60.2	20.3	42.9, 57.1	14.3	43.6, 56.4	12.7
60	45.2, 73.6	28.4	49.7, 69.7	19.9	52.9, 66.8	14.0	53.6, 66.1	12.5
70	55.4, 82.1	26.7	60.0, 78.8	18.7	63.1, 76.3	13.1	63.9, 75.6	11.7
80	66.3, 90.0	23.7	70.8, 87.3	16.5	73.8, 85.3	11.5	74.5, 84.8	10.3
90	78.2, 96.7	18.5	82.4, 95.1	12.7	85.0, 93.8	8.8	85.6, 93.4	7.8

Abbreviation: N, sample size.

Note: As described in the study design section, 200 subjects will receive a primary vaccination and 100 out of those 200 subjects will receive a boosting vaccination. In addition, 50 out of 100 active control subjects will receive a BPZE1 boost.

7.5 Analysis Sets

The Safety Analysis Set will consist of all subjects who have received at least 1 dose of the study vaccine and have any safety data available. Subjects will be classified according to the vaccine actually received. The primary safety analysis will be done on this analysis set.

The Intent to Treat Analysis Set will consist of all subjects who have been randomized to the study. Subjects will be classified according to the study group randomized. The data of subject disposition, demographics, and medical history will be summarized on this analysis set.

The Immunogenicity Analysis Set will include all the Intent to Treat subjects who received the prime dose of the study vaccine(s) and have contributed both pre- and at least 1 post-prime vaccination sample (mucosal or serum immunogenicity testing, respectively) for which valid results were reported and who have not received any component of a licensed pertussis vaccine in the 5 years through Day 113 of the study. Subjects will be classified according to the study vaccine received. For analysis of boosting, those subject who have received all vaccinations and have a pre- (Day 78 for mucosal and Day 85 for serum) and a post-boost immune sample (Day 113) for which valid results were reported will be utilized. Additional testing for maximum response will be assessed for those subjects who received all vaccinations and have both a baseline sample (screening or Day 1 depending on the sample type) and a sample at Day 113. Immune persistence will be assessed in those subjects who contribute to sampling at Days 169 and 254.

The Per Protocol Analysis Set will include all subjects in the Prime/Boost Immunogenicity Analysis Set, with the following exclusions:

- Data from all available visits for subjects following the receipt of unsuitable investigational product (either via dispensed/assigned or delivered).
- Data from all available visits for subjects found to be ineligible at baseline per Protocol Version 6.0.
- Data from all visits for subjects following the use of major immune-modulators, immune suppressants, receipt of blood products, or use of forbidden nasal solutions (eg, sprays, washes, neti pot) from 30 days prior to Day 1 through Day 113.
- Data from all visits for subjects following clinically significant protocol deviations that can affect the efficacy (immunogenicity) results.
- Data from any visit that occurs substantially out of window as defined by exceeding 30 days past the visit window or the time point whereby the follow-on visit should have occurred, whichever is most restrictive. Standard visit windows are described in schedule of events (Appendix 13.1).

For analyses using the Per Protocol Analysis Set, subjects will be grouped based on study vaccines actually received.

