7.7.1 Analysis of Primary Immunogenicity Endpoint

Summaries and analysis of immunogenicity data will be presented for the Immunogenicity and Per Protocol Analysis Set. For immunogenicity data in the prime period, subjects in the Prime Immunogenicity Analysis Set will be grouped into BPZE1 prime (A+B) and Boostrix prime (C+D) arms. For immunogenicity data in the boost period, subjects in the Boost Immunogenicity Analysis Set will be grouped to BPZE1 prime with BPZE1 boost (A), BPZE1 prime with no boost (B), Boostrix prime with BPZE1 boost (C) and Boostrix prime with no boost (D). In addition, as multiple antigens are being tested across vaccine combinations, all possible treatment group combinations will be displayed. For priming data analysis, the primary endpoint will be based on nasal mucosal immunogenicity change from screening, and for boost data analysis that will be based on screening and Day 78 prior to boost vaccination. The Immunogenicity and Per Protocol Analysis Sets will be used for sensitivity analysis.

The proportion and 95% CI of subjects who achieve seroconversion at Day 29 for prime vaccination and Day 113 for boost vaccination will be analyzed. Seroconversion is defined as a 2-fold increase over the baseline value or a 4-fold increase over the minimal limit of assay detection in S-IgA ELISA from nasal secretions for any of the pertussis-specific antibodies (S-IgA ELISA): PT, FHA, PRN, FIM 2/3, or BPZE1 whole cell extract). Baseline is defined as the value at screening.

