4.3.2. Immunogenicity Analysis Set

The Immunogenicity Analysis Set will include all the Intent to Treat subjects who received the prime dose of the study vaccine(s) and have contributed both pre- and at least 1 post prime vaccination sample (mucosal or serum immunogenicity testing, respectively) for which valid results were reported and who have not received any component of a licensed pertussis vaccine in the 5 years through Day 113 of the study. Subjects will be classified according to the study vaccine received. For analysis of boosting, those subjects who have received all vaccinations and have a pre (Day 78 for mucosal and Day 85 for serum) and a post boost immune sample (Day 113) for which valid results were reported will be utilized. Additional testing for maximum response will be assessed for those subjects who received all vaccinations and have both a baseline sample (screening or Day 1 depending on the sample type) and a sample at Day 113. Immune persistence will be assessed in those subjects who contribute to sampling at Days 169 and 254.

Subjects will be classified according to the study vaccine received and according to humoral and mucosal immunity samples as described. Subjects who discontinued from study will be classified according to randomized treatment arm. Subjects who missed a boost dose, will be classified to no boost treatment arm based on prime arm. Subjects who received wrong vaccination by mistake and discontinued from study will be classified according to actual vaccination, priority higher.

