8.2.1.6. The Geometric Mean Fold rise (GMFR) against each pertussis antigen (PT, FHA, PRN, FIM 2/3, and BPZE1 whole cell extract):

- On Days 29, 85, 113, 169, and 254 **over (pre-prime) baseline** based on Immunogenicity Analysis Set.
- On Days 113, 169, and 254 **over pre-boost** (Day 85) based on Immunogenicity Analysis Set.
- The maximum **over (pre-prime) baseline** on either Day 29 or 85 (post-priming response) based on Immunogenicity Analysis Set.
- The maximum **over pre-boost** (Day 85) on any of the Days 113, 169, or 254 (post-boost response) based on Immunogenicity Analysis Set.
- The maximum **during** the study based on Immunogenicity Analysis Set using (pre-prime) baseline.

8.2.1.7. The Geometric Mean Titer (GMT) against each pertussis antigen (PT, FHA, PRN, FIM 2/3, and BPZE1 whole cell extract):

- On Days 29, 85, 113, 169, and 254 based on Immunogenicity Analysis Set
- The maximum on Day 29 or 85 (after priming dose) based on Immunogenicity Analysis Set.
- The maximum after Days 113, 169, or 254 (after boosting dose) based on Immunogenicity Analysis Set.
- The maximum **during** the study based on Immunogenicity Analysis Set.

For systemic immunogenicity endpoints, unless otherwise specified, baseline will refer to the pre-prime baseline (defined as the last non-missing serum sample taken at Day 1/ Visit 1 prior to prime vaccination) and will be used for summaries based on Immunogenicity Analysis Set, as applicable. Pre-boost baseline is defined as the value collected on either Day 78/Visit 4 or Day 85/Visit 5 prior to boost vaccination and will be used for summaries based on Immunogenicity Analysis Set, as applicable. Data will be summarized based on the endpoint type as described in Section 3.2. Analyses will include the GMTs along with corresponding 95% CIs and GMFR at each time point and maximum titer or ratio at any time point.

For all systemic immunogenicity endpoints, summaries against each of the following Pertussis antigen specific antibodies will be provided based on results from IgA and IgG (PT, FHA, PRN, FIM2/3) separately and together. Summaries against BPZE1 whole cell extract will be provided based on results from IgG.

Listings will be provided for systemic immunogenicity data as collected based on the Immunogenicity Analysis Set.

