8.2.2. Secondary Mucosal Immunogenicity Analyses

Secondary mucosal immunogenicity endpoints are as described in Section 3.2.2.2.

Summaries and analyses will be the same as secondary systemic immunogenicity endpoints with the following exceptions:

1. the pre-boost baseline is defined as the value collected on Day 78/Visit 4 prior to boost vaccination. If the visit is missed on Day 78 but the subject arrives for boost vaccination, then a sample obtained prior to the vaccination will be used as the pre-boost value.
2. All mucosal immunogenicity endpoints will be calculated and summarized based on absolute titer response over baseline and by standardizing pertussis specific ELISA responses relative to non-pertussis specific total mucosal secretion of total IgA .

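### The maximum-response rule requires the Day 85 dose and a Day 113 sample even for the post-priming maximum, and the Day 113 and persistence denominators are not settled

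*Protocol*

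**What the plan says.** Entry to the Immunogenicity Analysis Set (Protocol 7.5, SAP 4.3.2) needs the prime dose, a valid pre-prime sample, at least one valid post-prime sample and no recent licensed pertussis vaccine. Both documents then add three narrower rules in nearly identical words.

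- **Maximum response.** "Additional testing for maximum response will be assessed for those subjects who received all vaccinations and have both a baseline sample", which continues "screening or Day 1 depending on the sample type) and a sample at Day 113". The endpoint lists include a maximum taken "on either Day 29 or 85 (post-priming response") for serum and "on either Day 29 or 78 (post-priming response") for nasal samples. SAP 8.2.1 repeats the serum version for titers: "The maximum on Day 29 or 85 (after priming dose) based on Immunogenicity Analysis Set".
- **Boosting.** Subjects need all vaccinations, a pre-boost sample (Day 78 nasal, Day 85 serum) and a Day 113 sample. Protocol 7.7.1 says that for the boost period "subjects in the Boost Immunogenicity Analysis Set will be grouped to BPZE1 prime with BPZE1 boost (A") and so on for the other arms. SAP 8.1 instead summarises Day 113 seroconversion on the general Immunogenicity Analysis Set. SAP 4.3.2 assigns subjects who missed the boost to the matching no-boost arm. SAP 8.2.2 adds a fallback for the nasal pre-boost value: "If the visit is missed on Day 78 but the subject arrives for boost vaccination, then a sample obtained prior to the vaccination" is used.
- **Persistence.** "Immune persistence will be assessed in those subjects who contribute to sampling at Days 169 and 254".

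Protocol 4.2.2 keeps subjects who stop vaccination on the same visit schedule. SAP 4.6 allows no imputation of missing immunogenicity results. SAP section 11 says the SAP changes nothing in the protocol's planned analyses.

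**The concern.** The post-priming maximum describes the response to one dose. Every sample it needs is taken before the boost. Making it depend on receiving that boost and returning four weeks later conditions a prime result on what happened after the prime. Reasons for stopping vaccination in Protocol 4.2.1 include adverse events and intercurrent illness, and some of these may be related to the prime.

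The tables could also look incoherent. A subject's maximum over Day 29 and the pre-boost visit cannot be below that subject's Day 29 value. Yet a post-prime maximum GMT on the restricted group could fall below the Day 29 GMT on the full set.

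For Day 113 the stake is the denominator of a primary endpoint. Two programmers working from the two documents could reach different ones. In a trial that only estimates, the denominator determines what each result describes.

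**Working it through.** **1. Samples used against samples required**

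| Endpoint | Enters the calculation | Required by the narrower rule but not used |
|---|---|---|
| Post-prime maximum, serum | Day 1; Day 29 and/or 85 | Day 85 dose, Day 113 sample |
| Post-prime maximum, nasal | Screening; Day 29 and/or 78 | Day 85 dose, Day 113 sample |
| Day 113 nasal seroconversion over screening | Screening; Day 113 | Day 78 sample (only if the boosting rule is applied) |
| Day 169 or Day 254 result over baseline | Baseline; that visit | The other late visit (only if both are required) |

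Only the first two rows follow from the text of both documents without a further choice of reading.

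**2. The plan's own figures.** Exact Clopper-Pearson limits reproduce all 20 cells of Protocol Table 7-1. For example, at 50% and N = 100 the limits are 39.83 and 60.17, a width of 20.34 (stated 20.3). The table assumes full arms.

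**3. Post-prime maximum, arms A+B (N = 200).** The documents give no loss rate, so take a share d = 5%, 10% or 20% lacking the Day 85 dose or the Day 113 sample, with prime data complete.

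- Subjects kept: 200(1 − d) = 190, 180, 160.
- Widening of a log-scale interval for GMT or GMFR, 1/√(1 − d) − 1: 2.6%, 5.4%, 11.8%.
- Selection: on the log scale the retained mean differs from the full mean by d × (retained mean − dropped mean). If the dropped subjects had half the retained GMFR (an assumption, for illustration), the retained value overstates the full one by a factor of 2^d: 1.035, 1.072, 1.149.

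**4. Day 113 seroconversion, if the boosting rule governs it.** Let 5%, 10% or 20% lack only the pre-boost nasal sample. The interval width at a 50% rate is:

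- N = 100: 95, 90, 80 kept; 20.3 becomes 20.9, 21.5, 22.8 points.
- N = 50: 48, 45, 40 kept; 28.9 becomes 29.5, 30.5, 32.4 points.

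Under SAP 8.1 this loss does not arise.

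**5. Persistence, if both visits are needed.** With a share m missed independently at each visit, 100(1 − m) are available per visit but 100(1 − m)² are kept. At m = 10% that is 90 against 81; at 20%, 80 against 64. If each visit stands alone, nothing is lost.

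**The case against.** The strongest reply is that the maximum-response sentence was never meant for the post-priming maximum. It follows the boosting rule, asks for a baseline and Day 113, and names no Day 29, 78 or 85 sample, which suits the maximum over the whole study. SAP 8.2.1 assigns the post-priming maximum to the Immunogenicity Analysis Set, whose entry conditions are light, and Protocol 7.7.1 puts prime-period data on a Prime set. That may well be the intention. But the sentence covers maximum response without limit, it sits inside the definition of the set that SAP 8.2.1 names, and neither document makes an exception.

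On Day 113 the reply largely stands. A reader might infer that subjects without a Day 78 nasal sample are certainly dropped. The documents do not support that. SAP 8.1 uses the general set, SAP 8.2.2 accepts a pre-dose sample at the boost visit, and the Protocol Table 13-1 footnote on nasal sampling also foresees one. Protocol 7.7.1 is itself unclear: it refers boost analysis to screening and Day 78, then defines the seroconversion baseline as screening. What remains is a conflict.

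On persistence, the sentence can equally be read visit by visit, and SAP 8.2.1 reports GMT and GMFR by day. Loss is a risk under one reading only.

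A reader might also infer from SAP 9.2.6 that Day 85 doses are expected to be withheld. That section only plans a table of such events and gives no rate.

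**Conclusion.** The point holds for the post-priming maximum: following the written rule sets aside complete prime responses because of later events. Selection is the main issue; the precision cost is modest, about 3% to 12% wider log-scale intervals if 5% to 20% are lost. These rates are assumptions. The size of any selection shift also depends on how different the dropped subjects are, which cannot be known in advance.

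For Day 113 the finding is an unresolved conflict between the protocol's boost set and the SAP's general set. It includes a clash within SAP 4.3.2, which requires all vaccinations for boosting yet places missed-boost subjects in the no-boost arm. For persistence the finding is ambiguity. It would be wrong to conclude that all three rules certainly remove subjects, or that the unneeded sample is always a later one: for Day 113 it is the earlier Day 78 sample.

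Day 29 seroconversion does not change. The trial tests no hypothesis, so no power or error rate is at stake.

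**What to change.** Amend the wording of Protocol 7.5 and 7.7.1 and SAP 4.3.2 and 8.1 before the Day 113 lock:

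- **Maxima using post-boost samples:** keep the all-vaccinations and Day 113 requirement here only.
- **Post-prime maximum:** all Immunogenicity Analysis Set subjects with a baseline and at least one valid Day 29 or pre-boost sample.
- **Day 113 seroconversion over screening:** valid screening and Day 113 samples.
- **Boosting and fold rise over pre-boost:** keep the pre-boost requirement, using the SAP 8.2.1 and 8.2.2 definitions.
- **Days 169 and 254:** each visit analysed on its own sample.
- **Missed boost:** reconcile the all-vaccinations condition with the SAP 4.3.2 sentence, so that each table has one stated rule on whether these subjects count and in which arm.

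The cost is text only, with no new data or visits. Denominators will differ slightly between endpoints and should be printed with each table.
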